9.2. Sample Size Determination

The primary efficacy parameter is the absence of a headache of moderate/severe intensity within 24 hours after taking double-blind study intervention during the prodrome. Based on the assumption of a response rate of 64% for the placebo group and 80% for the ubrogepant 100 mg group, 240 participants in each study intervention will provide at least 95% power to detect the

above intervention difference at the 2-sided 5% significance level. The nQuery Advisor 7.0 was used for the power calculation.

A blinded sample size re-estimation has been performed as planned. Given that 7% of participants had no determinable primary endpoint as observed based on the data cut of July 5, 2021, approximately 516 participants will be randomized to maintain the effect sample size of 480 participants.

The actual power will be higher with the crossover design as some participants will contribute 2 qualifying prodrome events during the double-blind treatment period.

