A sensitivity analysis will use multiple imputation approach to impute the missing headache occurrence or indeterminable status within 24 hours for each qualifying prodrome event. Specifically, for a participant who has not experienced headache of moderate/severity by time t_j (< 24 hours) after taking double-blind study intervention and has missing headache severity assessment at the next timepoint t_{j+1} , whether the participant will experience headache of moderate/severe intensity at t_{j+1} will be imputed based on other participants on the same treatment who have not experienced headache of moderate/severe intensity by time t_j but have observed headache severity assessment at t_{j+1} . So firstly, the missing headache severity assessment at time t_1 will be imputed. The missing headache at the following timepoints (2, 3, 4, 6, 8, 24, and 48 hours) will be imputed step by step similarly. The treatment difference between ubrogepant 100 mg and placebo will be estimated from the GLMM model for each imputed data set and combined across imputations to obtain the multiple imputation estimate using standard multiple imputation techniques.

Additional sensitivity analysis will impute participants with missing headache occurrence status within 24 hours as nonresponders for the qualifying prodrome event. For participants who go

through the 60-day double-blind treatment period with only 1 qualifying prodrome event due to lack of qualifying event or having an event but with no headache assessment, the missing data for the missing qualifying prodrome event will be considered as missing at random. For participants who discontinued the double-blind treatment period with only 1 qualifying prodrome event for other reasons, the missing data for the second qualifying prodrome event will be imputed based on the observed data for the second qualifying prodrome event from participants who use placebo to treat the second qualifying prodrome event. The treatment difference between ubrogepant 100 mg and placebo will be estimated from the GLMM model for each imputed data set and combined across imputations to obtain the multiple imputation estimate using standard multiple imputation techniques.

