**Figure 1. Study Schematic**

## 2.3 Treatment Assignment and Blinding

Subjects will be randomized to the following treatment sequences in a 1:1 ratio:

	First Qualifying Prodrome Event	Second Qualifying Prodrome Event
Treatment Sequence A	placebo	ubrogепant 100 mg
Treatment Sequence B	ubrogепant 100 mg	placebo

Participants randomized to Treatment Sequence A will receive placebo to treat their first qualifying prodrome event and ubrogепant 100 mg to treat their second qualifying prodrome event. For those randomized to Treatment Sequence B, they will receive the reverse: ubrogепant 100 mg to treat their first qualifying prodrome event and placebo to treat their second qualifying prodrome event.

Each blister card containing study intervention will be labeled with medication kit numbers. An automated Interactive Web-Response System (IWRS) will provide the site with the specific medication kit number(s) for each randomized participant at the time of randomization (Visit 2) and at Visit 3. Sites will dispense study intervention according to the IWRS instructions at these 2 visits. Sites will receive the IWRS confirmation notifications for each transaction. All notifications are to be maintained with the study source documents.

All study interventions will be provided in identical blister cards to maintain masking of the study. Tablets of ubrogепant 50 mg and placebo will be identical in appearance.

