## 2.4 Sample Size Determination

The primary efficacy parameter is the absence of a headache of moderate/severe intensity within 24 hours after taking double-blind study intervention during the prodrome. The original sample size of 600 participants randomized is based on the assumption of a response rate of 64% for the placebo group and 80% for the ubrogепant 100 mg group, 240 participants in each study intervention will provide at least 95% power to detect the above intervention difference at the two-sided 5% significance level. The nQuery

Advisor 7.0 was used for the power calculation. Assuming 20% of randomized participants will not experience a qualified prodrome event during the double-blind treatment period, 300 participants will be randomized to each treatment sequence.

A blinded sample size re-estimation has been performed as planned. Given that only 7% of participants, rather than the 20% originally assumed, had no determinable primary endpoint as observed based on the data cut of July 05, 2021, it was re-estimated that approximately 516 participants will need to be randomized to maintain the effective sample size of 480 participants.

The actual power will be higher with the crossover design as some participants will contribute 2 qualifying prodrome events during the double-blind treatment period.

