**Table 2. Analysis Populations**

Population	Definition	Study Intervention
Intent-to-treat (ITT)	All randomized participants. Participants will be summarized according to the randomized study sequence intervention.	Randomized
Safety	All treated participants who take $\geq 1$ administration of study intervention. Participants will be summarized according to the study intervention they actually received.	Actual received
Modified Intent-to-treat (mITT)	All randomized participants with $\geq 1$ assessment of headache occurrence within 24 hours after taking double-blind study intervention for at least 1 qualifying prodrome event during the double-blind treatment period. Participants will be summarized according to the randomized study intervention.	Randomized

For efficacy analyses, data will be analyzed according to participants' randomization assignments, regardless of actual study intervention received.

For safety data analyses, data will be analyzed according to participants' actual study intervention received (rather than as randomized).

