**Table 3. Missing data handling at prodrome level and within prodrome level**

Analyses	Missing prodrome event	Indeterminable endpoints within prodrome event level
Primary analysis	Ignore and no imputation	Set as missing and no imputation
Sensitivity analysis 1: NRI for indeterminable endpoints	Ignore and no imputation	Set as non-responder
Sensitivity analysis 2: imputation under MAR for indeterminable endpoints	Ignore and no imputation	Sequential multiple imputation
Sensitivity analysis 3: imputation under MNAR for missing prodrome events and under MAR for indeterminable endpoints	MNAR	Sequential multiple imputation
Sensitivity analysis 4: Period 1 only	Ignore and no imputation	Set as missing and no imputation

For sensitivity analysis 2, indeterminable endpoints will be imputed using multiple imputation under MAR. The determinations of the efficacy endpoints are described in the corresponding endpoints sections. Specifically for the primary endpoint, for a participant who has not experienced headache of moderate/severe intensity by time  $t_j$  after study intervention and has missing headache severity assessment at the next timepoint  $t_{j+1}$ , whether the participant will experience headache of moderate/severe intensity at  $t_{j+1}$  will be imputed based on other participants on the same treatment who have not experienced headache of moderate/severe intensity by time  $t_j$  but have observed headache severity assessment at  $t_{j+1}$ . Base will be used in the imputation logistic model. Base is a continuous variable denoting the percentage of absence of moderate/severe headache within time  $t_{j+1}$  during the screening period. So firstly, the missing headache severity assessment by time  $t_1$  will be imputed. The missing headache by the following timepoints (2, 3, 4, 6, 8, 24, and 48 hours) will be imputed step by step similarly. One hundred datasets will be imputed.

For sensitivity analysis 3, indeterminable endpoints will be imputed using multiple imputation under MAR, and endpoints in missing prodrome events will be imputed under MNAR. One hundred datasets will be imputed.

- For participants who go through the 60-day double-blind treatment period with only one qualifying prodrome event due to lack of qualifying event or having an event but with no headache assessment, the missing data for the missing qualifying prodrome event will be considered as missing at random using multiple imputation.

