#### **8.3.4 Sensitivity Analyses**

As alternative estimands for the primary study objective, the treatment condition, population, variable, and population-level summary will be the same as those in the primary estimand. However, the way to handle the discontinued participants with only one qualifying prodrome event and the approach to handle missing data within a prodrome event will be different. For participants who discontinued the double-blind treatment period with only one qualifying prodrome event, the missing data for the second qualifying prodrome event will be handled same as the primary analysis or imputed under MNAR. For indeterminable primary endpoint due to missing data within a prodrome

event, the primary endpoint will be set as missing, non-responder, or imputed using sequential multiple imputation. Missing data handling is described in Section 8.2.

A sensitivity analysis will impute participants with indeterminable status or missing headache occurrence within 24-hours recall as non-responders for the qualifying prodrome event. Data will be analyzed using the same primary GLMM model.

An additional sensitivity analysis will use multiple imputation approaches to impute the missing headache occurrence status within 24 hours under MAR for each qualifying prodrome event with indeterminable endpoints. Another sensitivity analysis will assume missing prodrome events as missing MNAR. The treatment difference between ubrogepant 100 mg and placebo will be estimated from the GLMM model for each imputed data set and combined across imputations to obtain the multiple imputation estimate using standard multiple imputation techniques applied to log odds ratio.

Analyses using only first period data will also be performed as a sensitivity analysis as mentioned in the previous section.

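### An event with no headache assessment is grouped with having no event, so the only MNAR analysis imputes it as MAR, and the plan gives two opposite treatments for it in the non-responder analysis

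*SAP*

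**What the plan says.** SAP 8.2, Table 3, separates two kinds of missing data: a missing prodrome event, and an endpoint that is indeterminable within an event. Sensitivity analysis 1 (non-responder imputation) ignores the first and sets the second to non-responder. Sensitivity analysis 3 is labelled MNAR for missing events and MAR for indeterminable endpoints.

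The text below the table then splits missing events in sensitivity analysis 3 by cause. For participants who go through the 60-day period with only one event, "due to lack of qualifying event or having an event but with no headache assessment", the missing event is imputed as MAR. For participants who discontinued with one event for other reasons, it is imputed from second-event placebo data. Protocol 9.4.1.2 has the same split, in the paragraph whose first sentence says that the analysis will "impute participants with missing headache occurrence status within 24 hours as nonresponders". Protocol 9.4.1.3 repeats it for the first and third secondary endpoints.

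Two other places bear on the same event. Protocol 9.4.1.2 counts a case as indeterminable when no moderate or severe headache was reported and the 24-hour recall is missing; it sets no minimum number of diary entries. SAP 8.3.4 imputes participants with "indeterminable status or missing headache occurrence within 24-hours recall as non-responders for the qualifying prodrome event".

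Efficacy analyses use the mITT population, which requires at least one "assessment of headache occurrence within 24 hours after taking double-blind study intervention for at least 1 qualifying prodrome event" (SAP Table 2).

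**The concern.** Having no second prodrome and having one that went unreported are different kinds of missingness. The first depends mainly on how often attacks occur. The second, if a dose was taken, is a post-dose non-report and may be related to outcome, for example when a severe attack stops the participant from using the diary. An MNAR analysis exists to test that possibility, and here the stated rule exempts it.

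The label also matters in sensitivity analysis 1. If the event counts as missing it drops out; if it counts as indeterminable it is a failure. Under the first reading, a participant with one early entry and no recall is a non-responder while one with no entry at all is left out. That choice should not remain open once data are seen.

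**Working it through.** **1. Handling of one event, dosed but with no headache assessment and no recorded rescue use, under each classification in Table 3:**

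| Analysis | If a missing prodrome event | If an indeterminable endpoint |
|---|---|---|
| Primary | ignored | set to missing |
| Sensitivity 1 (non-responder) | ignored | non-responder |
| Sensitivity 2 (MAR) | ignored | sequential imputation |
| Sensitivity 3 (MNAR label) | MAR if the participant goes through the 60 days; placebo-based if discontinued for other reasons | sequential imputation under MAR |
| Sensitivity 4 (Period 1) | ignored | set to missing |

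The primary analysis and sensitivity analysis 4 are the same in effect under both columns. Sensitivity analysis 1 gives opposite results. In sensitivity analysis 3, for a participant who goes through the 60 days, both columns lead to MAR, so reclassifying the event would not by itself add a stress test. The sequential imputation starts at the first timepoint, so it can handle an event with no entries; nothing technical requires such an event to be called missing.

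**2. The plan's own figures.** Protocol 9.2 assumes "a response rate of 64% for the placebo group and 80% for the" ubrogepant group. SAP 2.4 states that "240 participants in each study intervention will provide at least 95% power to detect the above intervention difference at the two-sided 5% significance level". With two independent groups and a pooled variance under the null:

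- mean rate 0.72; power = Φ[(0.16·√240 − 1.96·√(2·0.72·0.28)) / √(0.64·0.36 + 0.80·0.20)] = Φ[(2.479 − 1.245)/0.625] = Φ(1.975) = 97.6%, which meets the stated minimum.
- 480/0.93 = 516.1 and 480/0.80 = 600, matching the re-estimated and original totals.
- planning odds ratio = (0.80/0.20)/(0.64/0.36) = 2.25.

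None of these depends on the disputed rule.

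**3. Size under assumed shares.** The documents give no count of dosed but unassessed events. The nearest figure is "Given that only 7% of participants, rather than the 20% originally assumed, had no determinable primary endpoint" (SAP 2.4), which is per participant and covers every cause. I therefore assume shares s of treated events, from 0 to 7% per treatment. Counted as failures, the rate becomes p(1 − s):

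| s ubrogepant | s placebo | Rates | Odds ratio |
|---|---|---|---|
| 0 | 0 | 80.0% vs 64.0% | 2.25 |
| 3% | 3% | 77.6% vs 62.1% | 2.12 |
| 7% | 7% | 74.4% vs 59.5% | 1.98 |
| 3% | 1% | 77.6% vs 63.4% | 2.00 |
| 5% | 2% | 76.0% vs 62.7% | 1.88 |
| 7% | 0 | 74.4% vs 64.0% | 1.64 |
| 1% | 3% | 79.2% vs 62.1% | 2.33 |
| 0 | 5% | 80.0% vs 60.8% | 2.58 |

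Example, row 1% and 3%: (0.792/0.208)/(0.6208/0.3792) = 3.808/1.637 = 2.33.

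**4. Placebo-based imputation in sensitivity analysis 3.** Silent ubrogepant events take the placebo rate, so the ubrogepant rate is 0.80(1 − s) + 0.64s and placebo stays at 64%. This gives odds ratios of 2.18 (s = 3%), 2.14 (5%) and 2.10 (7%), against 2.25 under MAR.

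**The case against.** The best reply is that the plan already penalises much of this missingness. A dosed, silent event literally meets the indeterminable rule in Protocol 9.4.1.2, and SAP 8.3.4 and Table 3 then make it a non-responder in sensitivity analysis 1. Rescue use within 24 hours is non-response (SAP Table 4), and concomitant medication is reviewed at Visits 3 and 4, so rescue may be known without a headache entry. A participant who withdraws after a poor response falls under the other-reasons rule and gets placebo-based imputation. The flowchart that determines the endpoint (SAP Figure 2) is not shown in the available text and may settle the classification. The wording refers to having an event, not to taking a dose, and a qualifying event is defined without reference to dosing.

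Most of this stands. A reader might infer that the non-responder analysis ignores these events, or that no analysis penalises them. The documents do not support either: the SAP bullet sits only under sensitivity analysis 3, and the rules just listed catch some of these events. The position of the MAR wording directly after the non-responder sentence in Protocol 9.4.1.2 shows ambiguity, not exclusion.

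A reader might also infer that leaving out dosed participants without any assessment is an error. It is a prespecified mITT rule, and SAP 8.3.4 keeps the population the same across these analyses. What is missing is a count of such participants.

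The reply does not reach the participant who goes through the 60 days, takes a dose, records nothing and has no known rescue use. For that case sensitivity analysis 3 is MAR by stated rule, and sensitivity analysis 1 has two readings.

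**Conclusion.** The point holds in two parts. First, sensitivity analysis 3 does not stress silence after dosing for participants who go through the 60-day period; this is explicit in SAP 8.2 and in Protocol 9.4.1.2 and 9.4.1.3. Second, the text available does not settle whether a dosed event with no headache assessment is missing or indeterminable, and the answer decides between omission and failure in sensitivity analysis 1.

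The size is unknown because the number of such events is not given. With 80% and 64% response among assessed events, equal shares of 3% lower the non-responder odds ratio only from 2.25 to 2.12. Imbalance matters more and has no assured direction: 1.88 at 5% ubrogepant and 2% placebo, 2.33 at 1% and 3%. If silence follows severe attacks and the drug works, more silence on placebo is quite possible. So the figures do not show that the present rule favours ubrogepant; they show that the sensitivity analyses may leave this form of missingness untested. The primary analysis is unaffected. The change should be made, as it is cheap and removes a choice from the time of analysis.

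**What to change.** In SAP 8.2, with the same change in Protocol 9.4.1.2 and 9.4.1.3:

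1. Limit the MAR bullet to periods in which no study intervention was taken for a qualifying event. Base this on recorded dosing, which the eDiary captures (Protocol 6.4).
2. State in Table 3 that an event with recorded dosing but no headache assessment is an indeterminable endpoint, and so a non-responder in sensitivity analysis 1.
3. Add an explicit exception in sensitivity analysis 3: these events are imputed from placebo data of the same period, not by the sequential MAR imputation kept for partly observed events. Without it, step 2 would simply move them to another MAR rule. Using the same period matters because the existing placebo rule draws on second events only, while a silent event can be the first.
4. Report the number of these events by treatment and period, including dosed participants outside the mITT.

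If Figure 2 already classifies such events, align the text with it. The cost is wording, a reclassification of the records concerned and one table. The sensitivity estimates may be slightly less favourable; the primary analysis stays as it is.

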### **8.3 Primary Efficacy Endpoint(s) and Analyses**

#### **8.3.1 Primary Efficacy Endpoint**

The primary efficacy endpoint is the absence of a headache of moderate/severe intensity within 24 hours after taking double-blind study intervention during the prodrome.

#### **8.3.2 Handling of Missing Data for the Primary Efficacy Endpoint(s)**

Handling of missing data for the primary endpoint is described in Section [8.2](#).

#### **8.3.3 Primary Efficacy Analysis**

The primary hypothesis is stated as follows:

Primary Null hypothesis: Ubrogepant 100 mg is the same as placebo in the acute treatment of migraine when administered during the prodrome, as measured by the proportion of participants who do not develop headache of moderate/severe intensity within 24 hours after taking double-blind study intervention during the prodrome.

Primary Alternative hypothesis: Ubrogepant 100 mg is different from placebo in the acute treatment of migraine when administered during the prodrome, as measured by the proportion of participants who do not develop headache of moderate/severe intensity within 24 hours after taking double blind study intervention during the prodrome.

[figure not shown]
The main attributes of the primary estimand are summarized in [Table 4](#).

**Table 4. Summary of the Primary Estimand Attributes of the Primary Efficacy Endpoint**

Estimand Label	Attributes of the Estimand				
	Treatment	Endpoint	Population	Handling of Intercurrent Events	Statistical Summary
Primary	Treatment A: placebo Treatment B: ubrogepant 100 mg Placebo or ubrogepant 100 mg are assigned based on the 2x2 crossover to treat two qualifying prodrome events (Sequence A: placebo/ubrogepant 100mg, Sequence B: ubrogepant 100mg/placebo).	Absence of a headache of moderate/severe intensity within 24 hours after taking double-blind study intervention during the prodrome	mITT population (randomized participants with $\geq 1$ assessment of headache occurrence within 24 hours after taking double-blind study intervention for at least 1 qualifying prodrome event during the double-blind treatment period)	IE 1 at prodrome event level: data after the discontinuation will be handled by hypothetical strategy and assumed MAR. IE2 within prodrome event level: participants who took rescue medication within 24 hours will be counted as non-responder for the prodrome. IE3 within prodrome event level: indeterminable primary endpoint due to missing data during the prodrome will be set as missing and assumed MAR.	Treatment comparison (odds ratio) of percentages of absence of moderate/severe headache within 24 hours after taking ubrogepant 100mg vs placebo during the prodrome

The status of the primary endpoint will be determined as shown in [Figure 2](#).

**Figure 2. Determination of absence of moderate/severe headache within 24 hours (responder)**

The primary comparison between study intervention groups will be analyzed using a GLMM model with repeated measurements based on determinable data on the primary efficacy endpoint data. The GLMM model assumes a binary distribution for the response and uses a logit link. The analysis model will include study intervention period, and treatment as categorical fixed effects. An unstructured covariance matrix will be selected for the covariance matrix of the residual effect for the repeated measurements (corresponding to the two qualifying prodrome events) within a participant. The treatment difference in terms of odds ratio between ubrogapant 100 mg and placebo will be estimated from the GLMM model.

The carryover effect will be tested although no or very minimum carryover effect is expected as the minimum 7-day washout period is much longer than the 5 times of half-life. A similar GLMM model will be fitted to examine the carryover effect. The model includes period and treatment as categorical fixed effects, and period by treatment as interaction effect. The carryover effect will be tested using the confounded period by treatment interaction at 0.05 significance level. If the carryover effect is significant, the analysis will use the first period only data for the primary efficacy analysis. For sensitivity analysis purpose, first period only data analysis will be performed regardless of the significance level of the carryover effect using logistic regression model with treatment effect.

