9.4.1.2. Primary Analyses

The primary efficacy endpoint for the absence of a headache of moderate/severe intensity within 24 hours after taking double-blind study intervention during the prodrome will be analyzed using a GLMM based on determinable data on the primary efficacy endpoint. Specifically, the status of absence of a headache of moderate/severe intensity within 24 hours should be decided based on all observed data including headache reported at a series of scheduled timepoints, reported event-driven, 24-hour recall headache, and whether a participant took rescue medication. If a participant did not report moderate/severe headache and has a missing 24-hour recall assessment, that participant will be counted as indeterminable. This GLMM model assumes a binary distribution for the response and uses a logit link. The analysis model will include period, and treatment as categorical fixed effects. An unstructured covariance matrix will be used for the covariance matrix of the residual effect for the repeated measurements (corresponding to the 2 qualifying prodrome events) within a participant. The treatment difference in terms of odds ratio between ubrogepant 100 mg and placebo will be estimated from the GLMM model.

The carryover effect will be tested although no or very minimum carryover effect is expected as the minimum 7-day washout period is much longer than the 5 times of half-life. A similar GLMM model will be fitted. The model includes period and treatment as categorical fixed effects, and period-by-treatment interaction. The carryover effect will be tested using the confounded period-by-treatment interaction. If the carryover effect is significant, the analysis should use first period only data. For sensitivity analysis purpose, first period only data analysis will be performed regardless of the significance level of the carryover effect.

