A single-item measure assessing activity limitation based on a 24-hour recall will be administered as an additional health outcome measure. The measure will be used to evaluate activity limitation with a 5-level response ranging from "Not at all limited – I could do everything" to "Extremely limited." The measure will be administered at 24 hours after taking double-blind study intervention.

The following are general considerations for efficacy analyses:

- Efficacy analyses will be performed based on mITT population.
- Continuous variables will be summarized by number of participants with observed values (n), mean, standard deviation (SD), median, 1st and 3rd quartiles (Q1, Q3), minimum (min), and maximum (max).
- Categorical variables will be summarized by number of participants with observed values or events and percentages based on the specified population.
- The efficacy analyses will be performed using a GLMM in the observed binary response variable unless an imputation method is specified.
- The least squares mean (LSMEAN) estimates of the treatment effects for the primary and secondary endpoints alongside its 95% CI will be presented.

- All statistical hypothesis tests will be performed at the 2-sided 5% significance level.
- Efficacy analyses will be presented by treatment or study intervention randomized (placebo or ubrogepant 100 mg).

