## 12.0 Overall Type-I Error Control

To control the family-wise type I error rate at 0.05 for multiplicity across the hypothesis tests in the primary and secondary analyses, a hierarchical gatekeeping procedure will be followed.

Step 1: Test the primary hypothesis. If p-value <0.05, reject the primary hypothesis and go to the Step 2, otherwise stop.

Step 2: Test the first secondary hypothesis. If the first secondary hypothesis is rejected, go to Step 3, otherwise stop.

Step 3: Test the second secondary hypothesis. If 2nd secondary hypothesis is rejected, go to test third secondary hypothesis, otherwise stop.

Step 4: Test the third secondary hypothesis.

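### Switching the primary analysis to period-1 data after a significant carryover test raises the primary type I error from 5% to about 6.4–7.8%

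*SAP*

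**What the plan says.** SAP 8.3.3 makes a logit GLMM on both treated events the primary analysis: "The analysis model will include study intervention period, and treatment as categorical fixed effects". It then adds a pretest: "The carryover effect will be tested using the confounded period by treatment interaction at 0.05 significance level". The consequence of that pretest is: "If the carryover effect is significant, the analysis will use the first period only data for the primary efficacy analysis". Protocol 9.4.1.2 agrees, without giving the pretest level: "If the carryover effect is significant, the analysis should use first period only data".

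The error rates are set elsewhere. SAP 8.1 says: "All statistical hypothesis tests will be performed at the 2-sided 5% significance level". SAP 12.0 begins the hierarchy with: "Step 1: Test the primary hypothesis. If p-value <0.05, reject the primary hypothesis and go to the Step 2, otherwise stop". Its stated purpose is: "To control the family-wise type I error rate at 0.05 for multiplicity across the hypothesis tests in the primary and secondary analyses". Nothing in either document lowers the threshold to allow for the pretest.

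Two further statements matter. Both documents expect little or no carryover, because the washout of at least 7 days far exceeds five half-lives. Both also plan a period-1-only analysis as a sensitivity analysis whatever the pretest shows (Sensitivity analysis 4 in SAP Table 3).

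**The concern.** The procedure is a pretest followed by one of two tests, each at an unadjusted 5%. It keeps 5% overall only if the test used after a significant pretest still rejects 5% of the time in the trials where it is used. That is doubtful here. The pretest compares the sequences on the sum of their two periods, and period 1 is half of that sum. A chance imbalance in period 1 therefore makes the pretest significant and the period-1 comparison significant together.

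In a two-sequence, two-period design the interaction is also aliased with a plain difference between the sequence groups, as the SAP acknowledges. A significant pretest is therefore weak evidence of carryover in particular.

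The primary test opens the way to all three secondary endpoints. When the primary null is true, any excess error there passes directly into the family-wise rate claimed in SAP 12.0.

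**Working it through.** **Inputs.** From the documents: pretest at 0.05 (taken as two-sided) and the switch rule (SAP 8.3.3); primary test at two-sided 0.05 (SAP 8.1 and 12.0); response rates of 64% and 80%, 240 per intervention and 7% not determinable (Protocol 9.2, SAP 2.4). Assumed: within-participant correlation rho between the two events, which the documents do not give, shown for 0 to 0.6; and no true carryover, in line with the documents' expectation.

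**The plan's own figures first.** Mean rate = 0.72. SE under the null = sqrt(0.72 × 0.28 × 2/240) = 0.0410. SE under the alternative = sqrt((0.64 × 0.36 + 0.80 × 0.20)/240) = 0.0403. Power = Φ((0.16 − 1.96 × 0.0410)/0.0403) = 97.6%, consistent with the stated minimum of 95%. For the sample size, 480/0.93 = 516.1, matching about 516. These figures reproduce and are not in dispute.

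**Correlation between the two tests.** Let d1 and d2 be the between-sequence contrasts in periods 1 and 2, each with variance V and covariance rho·V.

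- Carryover contrast: S = d1 + d2, with variance 2V(1 + rho).
- Covariance of S with d1: V(1 + rho).
- Hence corr(S, d1) = (1 + rho)/sqrt(2(1 + rho)) = sqrt((1 + rho)/2).
- The two-period treatment contrast is proportional to d1 − d2, and its covariance with S is zero.

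So when the pretest is not significant, the two-period test still rejects 5% of the time. When the pretest is significant, the period-1 test does not.

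**Overall type I error.** With Zc the carryover statistic and Z1 the period-1 statistic,

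type I error = 0.95 × 0.05 + P(|Zc| > 1.96 and |Z1| > 1.96).

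At rho = 0 the correlation is 0.707 and P(|Z1| > 1.96 given |Zc| > 1.96) = 0.338. The total is 0.0475 + 0.05 × 0.338 = 0.0644. At rho = 0.6 it is 0.0475 + 0.05 × 0.582 = 0.0766.

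The analytic results were checked by simulating correlated binary pairs at 64% response, with 480/2 = 240 participants per sequence, on the logit scale. The complete-data column uses 200,000 trials per setting and the missing-data column 40,000.

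| rho | corr(Zc, Z1) | false rejection after a switch | overall, analytic | overall, simulated, complete data | overall, simulated, 20% of period-2 events missing |
|---|---|---|---|---|---|
| 0 | 0.707 | 33.8% | 6.4% | 6.5% | 6.4% |
| 0.2 | 0.775 | 40.8% | 6.8% | 6.9% | 6.7% |
| 0.4 | 0.837 | 48.8% | 7.2% | 7.3% | 7.0% |
| 0.6 | 0.894 | 58.2% | 7.7% | 7.8% | 7.4% |

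Outside this range the analytic value is 6.0% at rho = −0.3, 8.7% at rho = 0.9 and 9.75% in the limit rho = 1. The two-period test without the switch stays at 4.9% to 5.2% in the simulations.

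**The case against.** - **The rule is fully prespecified and leaves the analyst no discretion.** True, but following it exactly still gives more than 5%.
- **The switch is rare.** With no carryover it occurs in about 5% of trials. That alone adds 1.4 to 2.7 percentage points, because in those trials the period-1 test rejects 34% to 58% of the time.
- **The size depends on an unstated correlation and on complete data.** This stands as a limit on precision: the range is conditional on rho, and with 20% of period-2 events missing the top of it falls to 7.4%. The direction does not change.
- **The quoted error is two-sided.** Correct. By symmetry a false finding of benefit has half that probability, about 3.2% to 3.9% against a nominal 2.5%. The proportional excess is the same.
- **Period-2 data would not be lost.** Sensitivity analyses 1 to 3 would still use both events. They would leave only the primary test, but that is the test that decides the trial.
- **Power is hardly affected.** Overall power at 64% versus 80% stays near 99%. In the few trials that switch it drops to roughly 72% to 84%, depending on rho and on how correlated pairs are generated. Power is a side issue; the argument rests on type I error.
- **The switch guards against real carryover.** This is the best argument for it. However, the documents expect almost none, the pretest cannot separate carryover from a sequence-group difference, and the period-1 analysis is reported in any case.

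**Conclusion.** The concern holds. As written, the primary procedure has a two-sided type I error of about 6.4% to 7.8% for rho between 0 and 0.6, not 5%, and the family-wise claim in SAP 12.0 fails at its first step. The result rests on no true carryover, a two-sided pretest at 0.05 and an assumed rho. An excess remains at mildly negative rho and with a fifth of period-2 events missing. Because this concerns confirmatory error control on the primary endpoint, it should be corrected before unblinding.

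**What to change.** Delete the switching sentence in SAP 8.3.3 and in Protocol 9.4.1.2. State that the two-period GLMM with period and treatment is the primary analysis whatever the carryover test shows. Report the period-by-treatment estimate with its 95% confidence interval as a descriptive result, and keep the period-1 logistic model as Sensitivity analysis 4. This brings the type I error back to about 5%.

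No new data or analyses are needed. The cost is a new SAP version (the current one is 3.0) and a protocol amendment, for which Protocol 10.1.1 requires ethics committee approval. The reason should be documented and the change dated before unblinding. What is given up is the automatic response to real carryover. It would still show in the reported interaction estimate and in any disagreement between the period-1 and two-period results, and would then be handled as interpretation.
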